14.2 Secondary endpoint analysis

- Cumulative incidence of VTE in cancer patients with or without tissue factor bearing microparticles will be assessed for isoquercetin or placebo arms by a competing risk analysis and differences evaluated by the Gray test. We previously identified elevated tissue factor bearing microparticles as a significant risk factor for developing thrombosis with a cumulative incidence of 27-38%.⁴⁵ We also will evaluate whether isoquercetin reduces the cumulative incidence of symptomatic or proximal VTE in cancer patients with elevated tissue factor bearing microparticles. Based on our previous data, we anticipate that approximately 45% of patients enrolled will have elevated tissue factor bearing microparticles (N=278) and half will be randomized to placebo or isoquercetin. Based on estimated VTE rates of 20% in the placebo and 7% in the isoquercetin arms for individuals with high tissue factor bearing microparticles, the probability (power) to reject the null hypothesis is 0.84. The 1-sided type I error probability associated with this test of the null hypothesis is 0.025 (Fisher exact test).
- The cumulative incidence of major hemorrhage between the groups of patients treated with isoquercetin versus those without. Analysis will include time to first major bleed, overall incidence of bleeding and analysis of bleeding events over time.
- Overall survival according to randomization and tissue factor bearing microparticle status will be analyzed by Kaplan Meier and significance testing by log-rank analysis
- Cumulative incidence of total or symptomatic VTE at 2 months in all treatment arms (and according to tissue factor bearing microparticle status)
- Influence of isoquercetin on TFMP levels and change in TFMP levels over time. This will be analyzed by continuous measurement of difference using ANOVA approach.
- Cumulative incidence of VTE in patients with elevated TFMP and very elevated ddimer (>1500 mcg/L) overall and according to randomization.
- Correlation between complete blood count, d-dimer, ECOG, histology, stage, and TFMP levels will be determined by assessing the correlation coefficient by standard methods (Pearson or Spearman's coefficients).
- Linear regression modelling will be performed to assess the influence of chemotherapy, blood counts, growth factors, ECOG performance status on TFMP levels.
- Fine and Graey regression modelling will be performed to assess the influence of chemotherapy, blood counts, growth factors, ECOG performance status on VTE risk.
- Quality of Life (QOL) will be assesses using EORTC QLQ-30 version 3 which is an internationally validated and widely utilized questionnaire.⁵⁷ Scoring is based on responses to 30 questions dealing with functional quality and symptom burden. The questionnaire will be completed at baseline visit and end of treatment assessments. All are reported on a range 0-100; a high score represents a high level of functioning and QOL. We will analyze the data using analysis of variance techniques if the QoL has constant variance across groups (based on VTE rates and treatment groups). If not, we will use the Kruskal-Wallis test based on ranked QoL scores. If the questionnaire developers provide guidelines for scoring in the presence of missing data, we will

follow those guidelines. Alternatively, we will tally the number of questionnaires for which a particular data item is missing.

- Correlation between isoquercetin dose, plasma PDI inhibitory activity, and reduction in D-dimer or VTE incidence
- Cumulative incidence of VTE according to Khorana score³⁷
- At completion of phase II portion, we will compare the cumulative incidence of VTE of all 60 patients enrolled with similar historical population. As described above the overall cumulative incidence of VTE with similar inclusion criteria and design was 11%. We hypothesize the cumulative incidence of VTE in the phase II cohort will be 4%. Based on these assumptions, the power for this comparison is 80% (N=60 with a 1-sided alpha of 0.1 comparing 4% to historical 11% cumulative incidence rate using a Fisher exact test.)

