Appendix E: Special studies specimen collection and shipping report

1. OBJECTIVES

1.1 Study Design

The goal of this randomized, placebo controlled, phase II/III trial is to evaluate isoquercetin as a novel anticoagulant in patients with advanced cancer (pancreatic, non-small cell lung cancer, and colorectal cancer). The primary goal of the phase II study is to assess the relative reduction in D-dimer levels following isoquercetin administration and evaluate safety. Based on efficacy and safety data, a dose of isoquercetin will be selected for continued enrollment into a phase III trial in order to evaluate the effectiveness of isoquercetin in preventing VTE in cancer patients.

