1.3 Secondary Objectives

- To investigate the cumulative incidence of VTE according to tissue factor bearing microparticle status (and isoquercetin randomization). To evaluate the cumulative incidence of major hemorrhage between the groups of patients treated with isoquercetin versus placebo.
- To assess overall survival according to randomization and tissue factor bearing microparticle status
- To investigate the cumulative incidence of total or symptomatic VTE in all treatment arms (and according to tissue factor bearing microparticle status)
- To study the influence of isoquercetin on TFMP levels and change in TFMP levels over time.
- To evaluate the cumulative incidence of VTE in patients with elevated TFMP as well as very elevated d-dimer (>1500 mcg/L) overall and according to randomization.
- To assess for correlation between complete blood count, ECOG, histology, stage, Ddimer, and levels of tissue factor bearing microparticles
- To investigate the influence of chemotherapy, blood counts, growth factors, ECOG performance status on tissue factor bearing microparticle levels as well as VTE risk.
- Influence of VTE and isoquercetin on Quality of Life (QOL)
- To investigate the association between isoquercetin plasma concentrations, inhibition of protein disulfide isomerase activity, and reduction in D-dimer.
- To evaluate the efficacy of isoquercetin to reduce D-dimer or VTE in cancer patients based on levels of circulating tissue factor bearing microparticles or Khorana risk model
- To compare VTE rates at completion of phase II with historical rates of VTE in similar population

CONFIDENTIAL

This document is confidential. Do not disclose or use except as authorized.

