2.2 Study Disease and correlative studies background

The prothrombotic state associated with malignant disease has been a recognized entity since the 1800's. Almost 1 in 5 cases of venous thromboembolism (VTE) are thought to be related to cancer, and thrombosis is the second leading cause of mortality in cancer populations.³⁵ The risk of thrombosis attributed to the malignant state is not uniform across all histological diagnoses. There is a 10-fold greater rate of VTE among patients suffering from ovarian, brain, and pancreatic cancers compared to those with other histologies.³⁶ Randomized clinical trials have demonstrated a small absolute risk reduction in VTE with primary thromboprophylaxis of low molecular weight heparins. The absolute risk of VTE in these unselected cohorts is low (3-5%) and thus the benefit of daily injection and potential risk for bleeding has tempered enthusiasm for non-targeted thromboprophylaxis approaches. Different models and biomarkers are under investigation to identify those patients who are highest risk of developing thrombosis and thus would benefit the most from primary thromboprophylaxis. Khorana and colleagues developed and validated a scoring model that identified higher risk patients based on elevated platelet count, white blood cell count, body-mass index, and anemia.³⁷

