3.1 Eligibility Criteria

Participants must meet the following criteria on screening examination to be eligible to participate in phase 2 and 3 of the study:

3.1.1 Participants must have histologically confirmed malignancy that is metastatic or currently unresectable.

Eligible malignancies include:

- Adenocarcinoma of the pancreas (currently unresectable or metastatic)
- Colorectal (stage IV)
- Non-small cell lung cancer (currently unresectable stage III or stage IV)
- 3.1.2 Receiving or scheduled to receive first or second line chemotherapy (within 30 days of registration)
- 3.1.3 Minimum age 18 years. Because limited dosing or adverse event data are currently available on the use of isoquercetin in participants <18 years of age, children are excluded from this study but will be eligible for future pediatric isoquercetin trials.
- 3.1.4 Life expectancy of greater than 4 months.
- 3.1.5 ECOG performance status ≤ 2 (see Appendix B).
- 3.1.6 Patient must be able to swallow capsules (phase III only)
- 3.1.7 Participants must have preserved organ and marrow function as defined below:

Absolute neutrophil count \geq 1,000/mcL

CONFIDENTIAL This document is confidential. Do not disclose or use except as authorized. $\begin{array}{l} \mbox{Platelets} \geq 90,000/mcL\\ \mbox{PT and } \mbox{PTT} \leq 1.5 \ x \ institutional \ upper \ limit \ of \ normal\\ \mbox{Total bilirubin} < 2.0 \ mg/dl\\ \mbox{AST (SGOT)/ALT (SGPT)} \leq 2.5 \ X \ institutional \ upper \ limit \ of \ normal\\ \mbox{Creatinine} < 2.0 \ mg/dl \end{array}$

- 3.1.8 The effects of isoquercetin on the developing human fetus are unknown. For this reason, women of child-bearing potential and men must agree to use adequate contraception (hormonal or barrier method of birth control; abstinence) prior to study entry and for the duration of study participation. Should a woman become pregnant or suspect she is pregnant while participating in this study, she should inform her treating physician immediately.
- 3.1.9 Ability to understand and the willingness to sign a written informed consent document.

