10.4 TFMP levels and thrombotic risk

Absolute TFMP levels will be measured at baseline and 56 days. A correlation between TFMP and thrombotic risk will be investigated according to randomization arm (see Section 13.2).

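### Section 14.2 relates histology to TFMP level by a Pearson or Spearman coefficient, but cancer type is an unordered three-level variable, so the result depends on arbitrary coding

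*Combined protocol and SAP*

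**What the plan says.** Section 1.3 sets the secondary objective: "To assess for correlation between complete blood count, ECOG, histology, stage", together with D-dimer, against TFMP level. Section 14.2 gives one method for the whole list: "Correlation between complete blood count, d-dimer, ECOG, histology, stage, and TFMP levels will be determined by assessing the correlation coefficient by standard methods". The parenthesis that follows limits the method to "Pearson or Spearman's coefficients".

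Section 1.1 enrols "patients with advanced cancer (pancreatic, non-small cell lung cancer, and colorectal cancer". Section 2.2 uses histology to mean cancer type when it contrasts "ovarian, brain, and pancreatic cancers compared to those with other histologies". Section 3.1 sets the stage or extent for each type: "Colorectal (stage IV" for bowel, "Non-small cell lung cancer (currently unresectable stage III or stage IV" for lung, and unresectable or metastatic disease for pancreas.

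On the outcome side, section 10.4 says "Absolute TFMP levels will be measured at baseline and 56 days", so the variable to be explained is a continuous level.

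No other part of section 14.2 covers histology against TFMP:
- The linear regression for TFMP level lists chemotherapy, blood counts, growth factors and ECOG status. It includes neither histology nor stage.
- The ANOVA item concerns the influence of isoquercetin on TFMP and change over time.
- Kruskal-Wallis is named only for quality of life.
- No coding or indicator variables for cancer type are given anywhere.

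**The concern.** Pearson needs numbers and Spearman needs ranks. Blood counts, D-dimer and ECOG status supply them. Cancer type does not: someone must decide which of pancreas, colorectal and lung is 1, 2 and 3, and nothing in the disease or the plan fixes that choice. The reported coefficient then reflects the labels as well as the data. One real difference between cancers could be published as a positive, a negative or, for some patterns of means, a near-zero association.

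What is at stake is the histology part of a listed secondary objective. The question has substance, because TFMP is the trial's main candidate risk marker and section 14.1.2.4 itself names histology as a source of variation in thrombosis incidence.

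Stage raises a smaller and different question. It has an order, but section 3.1 ties it in part to cancer type, so a pooled stage coefficient can carry some of a difference between diagnoses.

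**Working it through.** The documents give no sample size, effect size or expected coefficient for this analysis, so there is no stated figure to reproduce. The check is whether the result depends on the coding.

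**1. Algebra for Pearson.** Assume equal numbers in the three types. Centre the codes 1, 2, 3 as −1, 0, +1, which have SD √(2/3). Let m₁ and m₃ be the TFMP means of the types labelled 1 and 3.

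- Covariance = (m₃ − m₁)/3
- r = (m₃ − m₁) / (3 × √(2/3) × SD) = (m₃ − m₁) / (√6 × SD)

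The type labelled 2 drops out of the numerator. The coefficient is a rescaled difference between whichever two types were given the outer labels.

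Numbers, assuming means 0, 0.8 and 0.2 with SD 1 within type:
- Overall mean = 1/3; variance between types = (0.1111 + 0.2178 + 0.0178)/3 = 0.1156; total SD = √1.1156 = 1.056
- Outer types differ by 0.2: r = ±0.2/(2.449 × 1.056) = ±0.08
- Outer types differ by 0.6: r = ±0.23
- Outer types differ by 0.8: r = ±0.31

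That is six values for one set of means.

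**2. Simulation for Spearman.** Inputs: 618 patients (section 14.1.2.4), split 206 per type (assumed; the documents give no split), log-normal TFMP with SD 1 on the log scale (assumed). With log-means (0, 1, 0) for types A, B and C:

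| Codes for A, B, C | Spearman | p |
|---|---|---|
| 1, 2, 3 | 0.002 | 0.96 |
| 1, 3, 2 | 0.337 | 7e-18 |
| 2, 1, 3 | −0.335 | 1.1e-17 |
| 2, 3, 1 | 0.335 | 1.1e-17 |
| 3, 1, 2 | −0.337 | 7e-18 |
| 3, 2, 1 | −0.002 | 0.96 |

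Kruskal-Wallis gives p=7e-21 for every row. Other assumed patterns over the six codings:
- Log-means (1, 0, 0): Spearman from −0.418 to +0.418; smallest absolute value 0.075 (p=0.064); Kruskal-Wallis p=2e-27.
- Log-means (1, 0.5, 0): Spearman from −0.311 to +0.311; smallest absolute value 0.113 (p=0.0051); Kruskal-Wallis p=5e-14.

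**3. Stage.** For a two-level ordered stage, reversing the codes only reverses the sign (±0.291 in the simulated example), so coding is not the problem. Confounding is possible. Assume 200 patients per type, lung 0.5 SD below the other two, half of lung at stage III, and no stage effect within any type. The total SD is √(1 + 0.25 × 2/9) = 1.027.
- All pancreas patients coded IV: stage III is 100 lung patients; stage IV is 100 lung and 400 others. Mean difference = 0.5 × 400/500 = 0.40 SD. With 1/6 of patients at stage III, r = 0.40 × √(5/36)/1.027 = 0.145.
- Half of pancreas coded as the lower stage: the share that is not lung is 100/200 in the lower stage and 300/400 in stage IV. Mean difference = 0.5 × (0.75 − 0.50) = 0.125 SD. With 1/3 at the lower stage, r = 0.125 × √(2/9)/1.027 = 0.057.

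A pure difference between diagnoses can therefore appear as a stage association of about 0.06 to 0.15 under these assumptions. Its sign depends on which cancer is higher.

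**The case against.** **The wording is loose and prescribes no 1-2-3 coding.** A 0/1 indicator such as pancreas against the rest would give a valid point-biserial coefficient, and an analyst would meet the problem on first use. It is true that a valid reading can be constructed. The plan does not state it, however, and it would answer a narrower question than the one about three types. The parenthesis also closes off a reading in which standard methods include a group comparison.

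**The figures rest on assumed means and an assumed split.** This stands. The documents give neither TFMP by cancer type nor case mix, so the coefficients are not forecasts. A reader might infer that a real difference between cancers will probably be reported as null. That is not supported: with log-means (1, 0.5, 0) even the least favourable coding gives p=0.0051, and a near-zero result needs particular patterns such as (0, 1, 0). The algebra in step 1 shows the dependence on labels without relying on the chosen means.

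**Stage should not be swept in.** This also stands. A reader might infer that the stage coefficient is equally meaningless, or that stage is nearly a proxy for diagnosis. Section 3.1 supports neither. Stage is ordered, stage IV or metastatic disease is eligible in all three cancers, and extent varies within both lung and pancreas. Only colorectal is fixed, so the confounding is partial and its size unknown.

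**The consequences are small.** The analysis has no stated alpha or power and feeds no decision. This is correct, and it limits the weight of the point without removing it.

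**Conclusion.** The point holds for histology. As written, section 14.2 assigns a correlation coefficient to an unordered three-level variable, and the resulting sign, size and p-value depend on arbitrary labels. The histology part of the section 1.3 objective cannot be answered that way, and no other analysis in the plan supplies the answer. This rests on two readings of the text: that histology means cancer type, as section 2.2 uses it, and that the two named coefficients are the whole method.

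For stage the conclusion is weaker. The coefficient is interpretable but partly confounded with cancer type, because colorectal patients are all stage IV and stage III is named only for lung. The amount cannot be computed without the case mix.

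The effect is confined to one secondary correlative analysis. The primary endpoints, the sample sizes and the decision to proceed to phase III are untouched.

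**What to change.** Amend the correlation item in section 14.2 as follows:
- **Blood counts, D-dimer, ECOG:** keep correlation coefficients with TFMP.
- **Histology:** compare TFMP across the three cancer types by Kruskal-Wallis, or ANOVA on log TFMP, and report group medians with confidence intervals. Kruskal-Wallis is the simpler default, since section 2.2 describes patients with no detectable TFMP, for whom a log needs a stated convention. An equivalent route is to add cancer-type indicators to the TFMP linear regression already planned.
- **Stage:** report the association adjusted for cancer type or stratified by it, and state how unresectable non-metastatic pancreatic cancer is coded. If the regression route is taken, entering stage with the cancer-type indicators handles both questions in one model.

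The cost is a sentence or two of SAP wording. No extra data, samples or patients are needed, and the change can be made at any time before the TFMP analysis.

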Pathologic changes in microparticle populations contribute to the hypercoagulability associated with various disease states, including malignancy. Microparticles are vesicular structures measuring less than 1 µm in size and are derived from a number of cells within the vascular compartment including leukocytes, platelets, red blood cells, and endothelial cells.³⁸ Some microparticles are considered procoagulant due to the exposure of negatively charged phospholipids on the external membrane leaflet for the support of thrombin generation.^{39,40} Subpopulations of microparticles also express tissue factor, the in vivo initiator of blood coagulation.^{41,42} Circulating tissue factor-bearing microparticles augment thrombus formation in animal models⁴³ and tumor-derived microparticles accumulate at the site of vascular injury.⁴⁴ Our group previously demonstrated that tissue factor bearing microparticles are elevated in cancer patients diagnosed with VTE and appear to be derived from the underlying tumor.⁴⁵ The association between tissue factor bearing microparticles and VTE has been described by several groups as well, including in a mouse model of vascular injury.^{44,46} Notably, in our study the 1 year cumulative incidence of thrombosis in cancer patients with increased tissue factor bearing microparticles was 34.8% versus 0% in those without detectable tissue factor bearing microparticles.⁴⁵ We recently completed a randomized phase II trial of low molecular weight heparin to prevent thrombosis in cancer patients with elevated tissue factor bearing microparticles.⁴⁷ The primary endpoint was the cumulative incidence of VTE at 60 days, as defined by symptomatic VTE or asymptomatic proximal DVT diagnosed by protocol-mandated bilateral lower extremity ultrasound. The overall cumulative incidence of thrombosis across the study was 11.3% at 60 days. The cumulative incidence of thrombosis in the high tissue factor bearing microparticle patients was 27% (N=11) compared with 5% (N=23) in those treated with low molecular weight heparin (P=0.06).

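### The 80% power given for the phase II comparison with the historical VTE rate belongs to a one-sample test against a fixed 11%, not to the Fisher exact test that section 14.2 names

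*Combined protocol and SAP*

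**What the plan says.** The last item of section 14.2 states that at the end of phase II "we will compare the cumulative incidence of VTE of all 60 patients enrolled with similar historical population". It takes the reference from earlier work, "As described above the overall cumulative incidence of VTE with similar inclusion criteria and design was 11"%, and sets the target: "We hypothesize the cumulative incidence of VTE in the phase II cohort will be 4"%. On these assumptions "the power for this comparison is 80"%, with the specification "N=60 with a 1-sided alpha of 0.1 comparing 4% to historical 11% cumulative incidence rate using a Fisher exact test". No size is given for the historical group. Section 1.3 lists the comparison as a secondary objective.

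The source of the 11% is the investigators' earlier randomized trial of low molecular weight heparin, described in section 2.2: "The overall cumulative incidence of thrombosis across the study was 11.3% at 60 days". For that trial's patients with high tissue factor bearing microparticles (TFMP), the rate "was 27% (N=11) compared with 5% (N=23) in those treated with low molecular weight heparin".

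**The concern.** A Fisher exact test compares two observed samples, so its power depends on the size of both. Section 14.2 gives one sample size and one fixed rate, which describes a one-sample test. If the analyst runs the test as named, uncertainty in the historical rate enters the comparison and power falls below the stated figure. At stake is how a non-significant result would be read: with 80% power it says something about a fall to 4%, and with about half that power it says little.

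The reference rate raises a second question. It pools heparin-treated and untreated patients, so it does not estimate the VTE rate expected without prophylaxis.

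**Working it through.** **Inputs.** From section 14.2: n = 60, rates 4% and 11%, one-sided alpha 0.10, stated power 80%. From section 2.2: overall rate 11.3%; high-TFMP patients 11 untreated and 23 on heparin, the latter at 5%. The historical size N is not stated and is varied below.

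**1. Reproducing the 80%.** Treat 11% as known and let X be the number of VTE in 60 patients.
- At 11%: P(X ≤ 3) = 0.0009 + 0.0068 + 0.0249 + 0.0594 = 0.092. Adding P(X = 4) = 0.1046 gives 0.197, above 0.10. The cut-off is therefore 3 or fewer.
- At 4%: P(X ≤ 3) = 0.781.
- The arcsine approximation, Φ[√60 × (2 arcsin √0.11 − 2 arcsin √0.04) − 1.282], gives 0.799.

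The stated figure is thus recovered, to within about 2 points, as a one-sample calculation.

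**2. The named test.** For each pair (x of 60, y of N), the one-sided Fisher p-value is the lower hypergeometric tail P(X ≤ x | x + y events in 60 + N patients). Power is the sum, over all pairs with p ≤ 0.10, of Bin(x; 60, 0.04) × Bin(y; N, 0.11).

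| Assumed historical N | Power |
|---|---|
| 60 | 0.416 |
| 76 | 0.455 |
| 102 | 0.521 |
| 200 | 0.593 |
| 1000 | 0.678 |
| 10000 | 0.722 |

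As N grows the power approaches the one-sample value of 0.781.

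Two of these sizes come from assumptions about the earlier trial, which had 11 + 23 = 34 high-TFMP patients in the two groups reported. If those were 45% of its patients (the share section 14.2 anticipates for phase III), N = 34/0.45 ≈ 76. If they were one third (the tercile definition in section 8.1), N = 34 × 3 = 102. Neither share is stated to be that trial's own.

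**3. Historical count taken as already observed.** If the historical result is held fixed near 11.3% (for example 8/71, 9/80 or 11/97), Fisher rejects at 2 or fewer of 60. Power is then P(X ≤ 2 | 4%) = 0.568. A larger fixed sample such as 38/335 restores the cut-off of 3 and a power of 0.781.

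**4. The reference rate.** Removing the 23 treated patients gives (0.113N − 0.05 × 23)/(N − 23).
- N = 76: (8.588 − 1.15)/53 = 14.0%
- N = 102: (11.526 − 1.15)/79 = 13.1%
- N from 150 down to 45: about 12% to 18%

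This treats cumulative incidences as simple proportions and rests on an assumed N, so it is indicative only.

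**5. Effect of a different reference on the rule.**

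| Reference | Alpha at ≤ 3 | Alpha at ≤ 4 | Cut-off at 0.10 level | Power at 4% |
|---|---|---|---|---|
| 11% | 0.092 | 0.197 | ≤ 3 | 0.78 |
| 13% (assumed) | 0.038 | 0.096 | ≤ 4 | 0.91 |
| 14% (assumed) | 0.024 | 0.064 | ≤ 4 | 0.91 |

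**The case against.** The strongest reply is that the calculation is sound and only its label is wrong. The entry quotes one sample size and one fixed rate. Section 14.1.1.7 attaches the same test name to a rule with no comparison group, nine or fewer VTE among 60. That rule reproduces as a one-sample binomial: P(X ≤ 9) = 0.927 at 10% and 0.045 at 25%, in line with the 92% and 5% stated there. This stands, and a reader who inferred that the 80% is an arithmetic slip would be going too far. It does not remove the need for a correction, because the first item of section 14.2 uses the same name for a genuine two-arm comparison. An analyst cannot tell from the name which test is meant here.

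A reader might also infer that the true power is about half, so that a real fall to 4% would be missed about half the time. That holds only if Fisher is actually run against a historical sample of roughly 76 to 102, and the documents do not give that size. Under the one-sample test the miss rate is about 22%.

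Nor is the heparin pooling a route to a false claim of benefit. Including treated patients at 5% lowers the reference and makes a reduction harder to show.

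**Conclusion.** The point holds as a mismatch between test and power. The 80% is approximately the power of a one-sample exact test against a fixed 11% (78%). The Fisher test named has less than 80% at every historical size computed: about 42% to 68% for assumed sizes from 60 to 1000 when historical sampling error is counted, and about 57% when a historical count near 11.3% from 71 to 97 patients is held fixed. The shortfall cannot be fixed more exactly without the historical size. That an unlimited historical sample gives 78% against a rounded 80% is not itself a meaningful gap.

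The consequence is limited. A reader might take the comparison to decide whether phase III goes ahead, but section 14.1.1.7 rests that decision on D-dimer and, failing that, on the nine-of-60 rule. The 4% versus 11% comparison appears in neither.

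The reference-rate point is separate and also holds: 11.3% is an all-patient rate that includes heparin-treated patients. The comparison is therefore conservative against isoquercetin, by an amount the documents do not allow one to fix.

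**What to change.** In the last item of section 14.2, do one of the following:

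- Name a one-sample exact binomial test against a fixed 11%, and state success as 3 or fewer VTE of 60, alpha 0.092, power 78%.
- Keep the Fisher exact test, state the size of the historical group, and report the power at that size.

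In either case, say that the 11% includes heparin-treated patients and justify that choice, or take the reference from the untreated participants of the earlier trial. If the reference changes, recompute cut-off, alpha and power together and do not carry over the 11% figures. At an assumed 13%, for example, the rule becomes 4 or fewer of 60, with alpha 0.096 and power 91%.

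The cost is a wording change and, under the first option, a stated power about 2 points lower. No design change or extra patients are needed. A new reference rate would need a tabulation from the earlier trial, which section 2.2 describes as the investigators' own.
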